 9. Personal history of cystic fibrosis, severe pancreatitis, pancreatic tumor, pancreatectomy or any other pancreatic disease leading to diabetes mellitus.
 10. Any known history of coronary artery disease including, but not limited to, history of myocardial infarction, stress test showing ischemia, history of angina, or history of intervention such as coronary artery bypass grafting, percutaneous coronary intervention, or enzymatic lysis of a presumed coronary occlusion)
 11. Abnormal EKG consistent with coronary artery disease or increased risk of malignant arrhythmia including, but not limited to, evidence of active ischemia, prior myocardial infarction, proximal LAD critical stenosis (Wellen's sign), prolonged QT interval (> 440 ms). Non-specific ST segment and T wave changes are not grounds for exclusion in the absence of symptoms or history of heart disease. A reassuring evaluation by a cardiologist after an abnormal EKG finding may allow participation.
 - EKG is only required for participants \geq 50 years old or with diabetes duration \geq 20 years
 - For participants < 50 years of age and < 20 years since diagnosis: History of prolonged QT interval, malignant arrhythmia, or congenital heart disease
 12. Congestive heart failure with New York Heart Association (NYHA) Functional Classification III or IV
 13. History of TIA or stroke
 14. Seizure disorder, history of any non-hypoglycemic seizure within the last two years, or ongoing treatment with anticonvulsants
 15. Recent history of diabetic ketoacidosis (DKA) or severe hypoglycemia in the last 6 months. Severe hypoglycemia is defined as an event that required assistance of another person due to altered consciousness, and required another person to actively administer carbohydrate, glucagon, or other resuscitative actions. This means that the participant was impaired cognitively to the point that he/she was unable to treat himself/herself, was unable to verbalize his/ her needs, was incoherent, disoriented, and/or combative, or experienced seizure or coma.
 16. History of more than 1 episode of DKA requiring hospitalization in the last 2 years
 17. History of more than 1 episode of severe hypoglycemia in the last year.
 18. Untreated or inadequately treated mental illness (indicators would include symptoms such as psychosis, hallucinations, mania, and any psychiatric hospitalization in the last year), or treatment with anti-psychotic medications that are known to affect glucose regulation.

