Once potential subjects have had time to review the consent document, they will meet with a study provider (MD or NP) that will explain the study, answer any questions, and administer informed consent. In the event that a volunteer is a patient of one of the study MDs or NPs, another staff MD or NP will answer questions and administer consent. Their designated contact will also have to meet with a study provider to hear what will be required of them if the subject participates in the study. Designated contact consent will be obtained in person or over the phone. Designated contact participants must have their own telephone in order to participate, either a personal cell phone or a household phone. If the designated contact's consent is obtained over the phone, two copies of the consent form will either be mailed or sent electronically to the designated contact (one to keep and one to return) and he/she will have the form in front of him/her during the phone consent process. The designated contact will return the signed consent form to the study staff either by mail or electronically, and the person obtaining informed consent will sign the document upon receiving it. All designated contacts will be trained in the symptoms of hypoglycemia and response to severe hypoglycemia, including the administration of glucagon. They will also be trained to recognize the symptoms of hyperglycemia, and when to contact study staff and local EMS. There will be separate consent documents for the subject and the designated contact. A licensed physician investigator will be available to speak with the subjects during the consent process in the event of an NP administering consent.

Study staff will answer any questions that the subjects and designated contacts may have during their participation. They will share any new information in a timely manner that may be relevant to the subject's willingness to continue participating in the trial. The subjects or designated contacts may choose to discontinue their participation at any time. If the designated contact chooses to discontinue their participation, another contact must be available, or study staff will make alternative arrangements to allow the subject to continue their participation in the study.

All enrollment and screening procedures and inclusion and exclusion criteria are the same for the Test Run and the RCT portion of the study.

V. Study Procedures

V. a. Screening Data

- Age
- Sex
- Race and ethnicity

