V. d. ii. Randomization of Study Visit Order

Once the subject has been enrolled and eligibility of subjects has been established, subjects will be randomized to one of the possible three visit orders. The Test Run period is not randomized; all subjects will only use the insulin-only iLet with BC222 lispro.

V. d. iii. General Study Policies for all Study Arms (including the Test Run):

- Subjects will remain within a geographic boundary established based on 250 miles from the designated base for study personnel at all times and will avoid any air travel.
- If the subject is sleeping at home, the designated contact (or one of the designated contacts, if two individuals are sharing the job) must also be at home. If the subject is traveling within the geographic boundary, the designated contact must go with them.
- Subjects and their designated contact will keep a charged mobile phone on their person (or at their bedside) at all times and will answer calls from the study staff.
- Study subjects will keep a Contour Next One glucometer easily accessible at all times in case a calibration is needed, and they will do all calibrations with this meter. They will keep a glucometer, fast-acting carbohydrates, and a glucagon emergency kit easily accessible at home in case their designated contact needs to use it.
- Subjects should use the study provided Contour Next One glucometer for all BG checks throughout the study. They are encouraged to check their BG at least four times a day, before meals and before bedtime. They will also be encouraged to check before exercise and at intervals during exercise, and for any symptoms of hypoglycemia. There are no restrictions on additional checks and subjects should check as often as they wish to confirm the accuracy of the Dexcom CGM and for safety.
- Subjects will wear leur-lock compatible infusion sets throughout the study.
- Subjects and their designated contact will not use any recreational drugs or drugs of abuse, other than alcohol. The need to take prescription drugs that dull the sensorium, reduce sensitivity to symptoms of hypoglycemia, or hinder appropriate decision-making may be grounds for exclusion from the trial or discontinuation of participation, a decision that will be made by the principal investigator.

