- Subjects may not take acetaminophen throughout the study due to potential interference with CGM sensing. Acetaminophen is known to interfere with the accuracy of the Dexcom CGM. Subjects will be instructed to contact study staff immediately if they inadvertently take acetaminophen or any drug containing acetaminophen (for example, combination cold medicines) for further instruction and guidance regarding use of the iLet.
- Subjects will not tamper with the bionic pancreas device in any way, including changing any settings.
- Subjects will keep their iPhone 6s charged, which will require charging at least once per day. In

addition, subjects will change the iLet batteries every two days and use only Lithium AAA batteries. Alkaline batteries should be avoided unless they are needed temporarily until lithium batteries can be placed.

- The bionic pancreas is not water resistant and therefore must be removed for showering. Subjects are urged to take appropriate precautions when they are disconnected from the bionic pancreas, including frequent BG checks and having carbohydrates readily available.
 - The Dexcom CGM transmitter is water resistant and can be left on for bathing and swimming.
 - Subjects may not remove the bionic pancreas for more than 1 hour at a time (e.g. for bathing) and may not remove it for more than 2 hours total in any 24-hour period.
- Any medical advice needed by the subjects during their participation, which is not directly related to BG control during the experiment, should be obtained by them in the usual manner with their primary care physician or endocrinologist.
 - If a subject develops an illness during the experiment, they can seek medical care as usual. As long as the subject is not hospitalized, the study can be continued. If the subject is unable to eat for a period exceeding one day, they must notify study staff so that the medical staff can assess the safety of continuing in the study.
- Subjects will be asked to report all hypoglycemia, carbohydrate interventions, any nausea and/or vomiting, any other adverse events, time spent exercising, and any unscheduled infusion set changes, alcohol use, and other questions through a daily email survey.
- Subjects may participate in any activities that they wish, as long as they abide by the policies above.

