- There are no restrictions of any kind on diet or exercise in all three arms in the RCT portion of the study and the Test Run period, although subjects should attempt to maintain similar dietary habits and exercise habits during each arm of the study. The bionic pancreas must be kept dry during exercise.
- Subjects may choose to withdraw from the study at any time. If they withdraw from the study, they should contact a provider immediately who will help them transition to their own insulin regimen safely.

Test Run Policies Only

- Subjects in the Test Run period will be under supervision of study staff during the day. Subjects will be allowed to leave the clinic but will be restricted to the area immediately surrounding the clinic (e.g. within walking distance) and must be in contact with study staff regarding their location.
- While in the clinic, there will be no restrictions on physical activity and subjects will be encouraged to remain as physically active as they are in their normal life.
- Subjects will be required to check a BG at 1 and 2 hours after each meal announcement on all three days of the Test Run, including meal challenges and any other meal announcements delivered.
- Subjects will complete the meal challenges on days 2 and 3 of the Test Run period, following the same protocol as the RCT portion of the study.
- Subjects will be discharged from the clinic at the end of each day to home with a designated contact. During the first two nights at home, subjects will be instructed to check an overnight BG.

V. d. iv. Remote Monitoring

Local Alarms

- All alarm settings will be the same for the Test Run, the RCT portion of the study and during meal challenges.
- Alarms will sound and a visual alert will appear on the screen of the G5 mobile app when the CGM glucose is ≤ 70 mg/dl and the BP will alarm when the CGM glucose is ≤ 50 mg/dl.
 - Participants will be trained to test their BG with the study glucometer in response to such an alarm and take any necessary measures to treat hypoglycemia.

- Participants will be trained on troubleshooting for various scenarios that could lead to low threshold alarms. For instance, a threshold alarm could be due to true hypoglycemia, inaccurate CGM readings, or a compression artifact at the site of the sensor.
 - The first step for all glucose-related alarms will be to perform a fingerstick BG measurement.

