- All equipment will be collected and cleaned. The Dexcom G5 transmitter will be cleaned using the validated cleaning and disinfecting procedures.
- Subjects will be reminded to bring their own pump, supplies and insulin to this visit.
- A provider (MD or NP) will review the last several hours of insulin dosing and assist the subject in resuming their usual care.

V. d. vi. Response to Hypoglycemia

- The response to hypoglycemia is the same for the Test Run, the RCT portion of the study and before, during and after the meal challenges.
- The Dexcom G5 app will generate a local low glucose threshold alarm if the subject's CGM value is ≤ 70 mg/dl and the iLet BP will generate an alarm for a CGM < 50 mg/dl.
- In all study arms subjects are encouraged to check their BG for any symptoms of hypoglycemia.
- Subjects are encouraged to treat hypoglycemia according their usual practice or according to the "rule of 15s": take 15 grams of rapid acting carbohydrate and recheck in 15 minutes, then repeat as needed.
- The designated contact will be trained in the signs and symptoms of hypoglycemia and the protocols for treating it. They will also be trained in the use of the glucagon rescue kit. If they should find the subject unresponsive they are to use the glucagon rescue kit and call 911.
- Subjects may contact a study provider (RN, MD or NP) for advice at any time, and may contact the troubleshooting support team, as they wish. Subjects will be assisted in checking the bionic pancreas for any malfunction and correcting any problems that are found.
- If no correctable fault is found, but there is doubt regarding the correct function of the bionic pancreas system, an entirely new backup bionic pancreas system may be brought to the subject's location by study staff.
- If a subject experiences a seizure or unconsciousness associated with hypoglycemia in the study, his or her participation in the study will be discontinued.

V. d. vii. Response to Hyperglycemia

- The response to hyperglycemia is the same for the Test Run, the RCT portion of the study and before, during and after the meal challenges.
- The Dexcom G5 app will generate a local high glucose threshold alarm if the subject's CGM value is > 250 mg/dl. Subjects will be instructed to check their insulin infusion site and their bionic pancreas for normal operation any time BG is greater than 250 mg/dl. If there is any suspicion of insulin infusion set malfunction, the site should be replaced.

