we believe that the risk of hypoglycemia will be less than or equal to the risks that they are exposed to on a daily basis while living with type 1 diabetes outside of the trial.

Even though no increase in hypoglycemia was observed in subjects with T1D using BC222 inuslin lispro under MDI or open-loop regimen, there may be an increased risk of hypoglycemia with the ultra-rapid BC222 insulin lispro, which is expected to have a faster onset than rapid acting analogs. Subjects will be trained on the recognition and treatment of hypoglycemia, and the risk of using an ultra-rapid insulin will be explained to them. We anticipate the bionic pancreas will adapt to the faster pharmacokinetic profile of BC222 insulin lispro, and that hypoglycemia will not be higher than what the insulin-only bionic pancreas is able to achieve with rapid-acting insulin. We believe that the risk of hypoglycemia is further mitigated by keeping the PK parameter settings of the iLet at 65 minutes, despite the possibility BC222 is faster than that. The Test Run period using BC222 lispro in the iLet in a supervised setting will be completed and reviewed for safety prior to initiating any outpatient experiments using BC222 lispro.

There is a risk of hyperglycemia. This risk is expected to be similar to or less than the risk during the subjects' lives outside of the trial based on data from earlier trials in subjects with type 1 diabetes.

VIII. Potential Benefits

Based on evidence from previous trials of the bionic pancreas and the design of this trial, subjects enrolled in the study may benefit from a reduction in risk of hypoglycemia and hyperglycemia and a better mean glucose than they typically achieve.

Subjects are expected to benefit in all arms of the study from the formal involvement of a designated contact who will serve as a backup to respond to any overnight threshold alarms to which the subject does not respond.

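### The glucagon kit is required only at home, although the designated contact must travel with the participant and use the kit wherever the participant is found unresponsive

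*Combined protocol and SAP*

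**What the plan says.** Section V.d.iii (General Study Policies for all Study Arms) has participants keep a glucometer, fast-acting carbohydrates and "a glucagon emergency kit easily accessible at home in case their designated contact needs to use it". The sentence just before it deals with the calibration glucometer and requires that meter to be within reach at all times, not only at home.

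The same section limits participants to a 250-mile radius. On the contact's whereabouts it says: "If the subject is traveling within the geographic boundary, the designated contact must go with them". It closes its activity rules with "Subjects may participate in any activities that they wish, as long as they abide by the policies above".

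Section V.d.vi (Response to Hypoglycemia) states the contact's duty: "If they should find the subject unresponsive they are to use the glucagon rescue kit and call 911". Section IV.b says that all contacts are trained in "response to severe hypoglycemia, including the administration of glucagon". It does not mention where the kit is kept or whether it is carried.

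**The concern.** The kit is there for the contact to use. The contact has to leave home with a participant who travels, but the rule on where the kit is kept stops at home. The instruction in V.d.vi can be carried out only if the kit is where the contact is, and the visible text does not ensure that.

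What is at stake is the contact's means of giving glucagon during an uncommon but serious event. The randomized arms use the insulin-only configuration at home (Section II, Aim 1), so the device gives no glucagon. One arm uses an ultra-rapid insulin for which Section VII says "there may be an increased risk of hypoglycemia with the ultra-rapid BC222 insulin lispro, which is expected to have a faster onset" than the rapid-acting analogs. The same section expects hypoglycemia in that arm to be no higher than with rapid-acting insulin, and keeps the algorithm's 65-minute PK setting as a mitigation. The concern therefore does not depend on any predicted excess of events.

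**Working it through.** No arithmetic on trial data applies. The check is a reading of the provisions side by side, with a count of the mentions of the kit.

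**1. Mentions of the kit** (called an emergency kit or a rescue kit)

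| Section | Mentions | Location given | Carrying required |
|---|---|---|---|
| V.d.iii | 1 | Home | No |
| V.d.vi | 2 | None | No |
| Total | 3 | 1 of 3 (home) | 0 of 3 |

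Glucagon is mentioned elsewhere as a pump hormone, in the definitions of severe hypoglycemia, and in the contact's training. None of those places deals with where the kit is.

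**2. The rules taken together**

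- Kit: required at home (V.d.iii).
- Contact: at home when the participant sleeps there, and alongside the participant when the participant travels (V.d.iii).
- Contact's duty: use the kit and call 911 on finding the participant unresponsive, with no limit of place (V.d.vi).

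When the participant is at home, all three are consistent. When the participant is travelling, the second and third apply away from home and the first does not. That is the gap.

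**3. Is 'at home' shorthand for 'always to hand'?** Probably not. V.d.iii uses a broader phrase when it means one: the calibration meter is to be accessible at all times, and phones are to be on the person or at the bedside at all times. The narrower wording for the kit reads as a location rule.

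**4. Which part of the trial is affected?** In the Test Run, participants stay in or near the clinic under staff supervision by day and are discharged home with a contact at the end of each day, so the gap has no practical effect there. It concerns the home-use randomized arms.

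**5. What else protects a participant who is away from home?**

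- Eligibility: Section III.b excludes "Recent history of diabetic ketoacidosis (DKA) or severe hypoglycemia in the last 6 months", and also more than one severe episode in the last year.
- Local alarms (V.d.iv): the CGM app sounds at 70 mg/dl, and "the BP will alarm when the CGM glucose is ≤ 50 mg/dl". Participants are trained to check their glucose and take carbohydrate.
- Remote monitoring (V.d.iv): an alert is raised when CGM glucose is below 50 mg/dl for 15 minutes. Staff phone the participant, then the contact. If neither is reached and hypoglycemia continues, emergency services may be sent.
- The contact calls 911 (V.d.vi).

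**6. Where those protections thin out.** V.d.iv lets a participant remain where network coverage is poor. Staff then cannot watch for severe lows and instead phone every 2 hours. III.b excludes people who live in or frequent poorly covered areas, but not an occasional trip to one. Emergency dispatch is directed to places the participant is known to frequent, which a travel destination may not be.

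**7. Size.** The documents give neither the time participants spend away from home nor a rate of unresponsive events. No expected number of affected days or events can be calculated, and none is offered.

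**The case against.** The strongest reply has three parts.

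**The missing instruction may exist elsewhere.** Section IV.b refers to contact training and to a separate consent document for the contact, and advice on carrying the kit would naturally sit there. Those texts are not among the documents. This stands, and it limits the claim to what the supplied protocol says. If the training already covers the point, the protocol should be brought into line with it.

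**The duty implies the means.** A contact told to use the kit and required to travel could be expected to infer that the kit comes too, and nothing forbids taking it. This stands in part: the text does not bar good practice. But a safety instruction should not depend on an inference that runs against its own stated location.

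**Home is where the contact is mostly needed.** Section VIII describes the contact as a backup for overnight alarms, and V.d.iii ties the contact to the home on nights spent there. This is fair, and it narrows the gap to travel and nights away. It does not close it, because V.d.iii provides for travel expressly.

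A reader might go further and infer that participants away from home have no rescue, or that the plan is unsafe. The documents do not support that. Self-treatment, alarms, monitoring and the 911 call all apply away from home, and Sections VII and VIII expect hypoglycemia risk to be no greater than in participants' daily lives.

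**Conclusion.** The point holds as a gap in the wording of a safety rule. In the supplied text the kit has to be at home only, while the person meant to use it must go where the participant goes and is told to use it there. The randomized arms could be run exactly as written with the contact away from home and without the kit.

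The risk is small and cannot be quantified. The remaining exposure is an unresponsive episode on a trip, most relevant where remote monitoring has lapsed. Endpoints, analysis and the Test Run are unaffected. The conclusion assumes that no training or consent text already tells contacts to carry the kit. If one does, only the alignment of the protocol remains. The change is optional and is raised because it is so cheap.

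**What to change.** In Section V.d.iii, extend the location so that the kit is easily accessible at home, *and taken along whenever the subject is traveling with the designated contact or sleeping away from home*. Naming both situations matters because the section does not define travelling. The glucometer and carbohydrates in the same sentence are then covered too. Repeat the line in the contact's glucagon training under Section IV.b.

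The cost is one clause, one line of training, and the burden of carrying a kit on trips. No extra staff, visits or procedures are needed.
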